8.1. Discontinuation from Study Treatment

8.1.1. Permanent Discontinuation from Study Treatment

Discontinuation of the investigational product for abnormal liver tests **should be considered** by the investigator when a patient meets one of the following conditions after consultation with the Lilly-designated medical monitor:

- alanine aminotransferase (ALT) or aspartate aminotransferase (AST) >8X upper limit of normal (ULN)
- alanine aminotransferase or AST >5X ULN for more than 2 weeks
- alanine aminotransferase or AST >3X ULN and total bilirubin level (TBL)
 >2X ULN or prothrombin time >1.5X ULN
- alanine aminotransferase or AST >3X ULN with the appearance of fatigue, nausea, vomiting, right upper-quadrant pain or tenderness, fever, rash, and/or eosinophilia (>5%)
- alkaline phosphatase (ALP) >3X ULN
- alkaline phosphatase >2.5X ULN and TBL >2X ULN
- alkaline phosphatase >2.5X ULN with the appearance of fatigue, nausea, vomiting, right quadrant pain or tenderness, fever, rash, and/or eosinophilia (>5%)

In addition, patients will be discontinued from the investigational product in the following circumstances:

- Neutrophil (segmented) counts (see Section 9.4.5.3 for information on monitoring for neutropenia)
 - o <500 cells/uL
 - ≥500 and <1000 cells/uL (based on 2 test results; the second test performed within 1 week from knowledge of the initial result).
 - ≥1000 and <1500 cells/uL (based on 3 test results) and an infection that is not fully resolved.
 

- Total white blood cell count <2000 cells/μL.
- Lymphocyte count <500 cells/μL.
- Platelet count <50,000 cells/μL.
- Changes in blood pressure defined as sitting systolic blood pressure at ≥160 mm Hg plus ≥20 mm Hg increase from baseline (Visit 2 [Week 0]), and/or diastolic blood pressure at ≥100 mm Hg plus ≥10 mm Hg increase from baseline, that do not respond following maximal allowed intervention (see Section 9.4.5.1 for information on monitoring hypertension).

- The patient experiences a severe AE, an SAE, or a clinically significant change in a laboratory value occurs that, in the opinion of the investigator, merits the discontinuation of the investigational product and appropriate measures being taken. In this case, Lilly or its designee is to be notified immediately.
- Clinically significant systemic hypersensitivity reaction after SC administration of investigational product that does not respond to symptomatic medication or results in clinical sequelae.
- The patient becomes pregnant.

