- The patient develops a malignancy. **Note**: Patients may be allowed to continue if they develop no more than 2 nonmelanoma skin cancers over any 12-month period during the study.
- The patient develops symptoms suggestive of a lupus-like syndrome and is positive for antibodies against double-stranded DNA.
- If the patient, for any reason, requires treatment with another therapeutic agent that has been demonstrated to be effective for the treatment of PsA or Ps, discontinuation from the study occurs prior to introduction of the new agent.
- Enrollment in any other clinical trial involving an investigational product or enrollment in any other type of medical research judged not to be scientifically or medically compatible with this study.
- The patient develops active suicidal ideation with some intent to act with or without a specific plan (yes to question 4 or 5 on the "Suicidal Ideation" portion of the C-SSRS) or develops suicide-related behaviors as recorded on the C-SSRS. It is recommended that the subject be assessed by a psychiatrist or appropriately trained professional to assist in deciding whether the subject is to be discontinued from the study.
- The patient develops any condition or contraindication as addressed in the local labelling for adalimumab that would preclude the patient from continuing in this protocol.
- The investigator or attending physician decides that the patient should be withdrawn from the study.
- The patient requests to be withdrawn from the study.
- The investigator or Lilly stops the patient's participation in the study or Lilly stops the study for medical, safety, regulatory, or other reasons consistent with applicable laws, regulations, and good clinical practice (GCP).
- The patient becomes HBV DNA positive. The patient should be referred to a specialist physician.
- The patient is diagnosed with an active TB infection.

If in consultation with Lilly or its designee noncompliance is deemed to be significant or if further noncompliance occurs, the patient may be discontinued from the study (see Section 10.3.2.4 Treatment Compliance).

Any patient who permanently discontinues the study treatment for any reason will stop treatment and continue to the ETV prior to entering the Post-Treatment Follow-Up Period (Period 3).

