8.2. Discontinuation from the Study

Some possible reasons that may lead to permanent discontinuation include:

- enrollment in any other clinical trial involving an investigational product or enrollment in any other type of medical research judged not to be scientifically or medically compatible with this study
- participation in the study needs to be stopped for medical, safety, regulatory, or other reasons consistent with applicable laws, regulations, and good clinical practice (GCP)
- investigator decision
 - o the investigator decides that the patient should be discontinued from the study
 - o if the patient, for any reason, requires treatment with another therapeutic agent that has been demonstrated to be effective for treatment of the study indication, discontinuation from the study occurs prior to introduction of the new agent
- subject decision
 - o the patient or the patient's designee requests to be withdrawn from the study

Any patient who discontinues the study for any reason will stop treatment and continue to the ETV prior to entering the Post-Treatment Follow-Up Period (Period 3).

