[D13] Enrollment in any other clinical trial involving an investigational product or enrollment in any other type of medical research judged not to be scientifically or medically compatible with this study	Monitor	Monitor's list
[D14] The patient develops active suicidal ideation with some intent to act with or without a specific plan (yes to question 4 or 5 on the "Suicidal Ideation" portion of the C-SSRS) or develops suicide-related behaviors as recorded on the C-SSRS.	Monitor and Stats	Monitor's list, or, If patient still receives study treatment on the same day or after the date with a yes to question 4 or 5 on the "Suicidal Ideation" portion of the C-SSRS or develops suicide-related behaviors as recorded on the C-SSRS.
[D15] The patient develops any condition or contraindication as addressed in the local labelling for adalimumab that would preclude the patient from continuing in this study protocol.	Monitor	Monitor's list

Important Protocol Violation Category/Subcategory	Source to Identify Protocol Violation	Statistical Programming Guidance for Clinical Study Report
[D16] The investigator decides that the patient should be withdrawn from the study	Monitor	Monitor's list
[D17] The patient requests to be withdrawn from the study	Monitor	Monitor's list
[D18] The investigator or Lilly stops the patient's participation in the study or Lilly stops the study for medical, safety, regulatory, or other reasons consistent with applicable laws, regulations, and GCP.	Monitor	Monitor's list
[D19] The patient becomes HBV DNA positive.	Monitor	Monitor's list
[D20] The patient is diagnosed with an active TB infection.	Monitor	Monitor's list
Category: Study Procedures		
Sub-Category: Excluded Con-meds	Monitor and Stats	Either from monitor's list, or If patient takes prohibited concomitant medication. Note: Prohibited concomitant medication (with details of dose restrictions) will be provided by medical in a separate file.
Sub-Category: Lab/Imaging Criteria		
Missing lab chemistry and hematology: missing baseline or not having at least 1 post-baseline	Monitor and Stats	Monitor's list; or If missing lab chemistry and hematology baseline or not having at least 1 post-baseline
Sub-Category: Other		
Missing ACR or PASI	Monitor and Stats	Monitor's list; or If missing any ACR or PASI data at any visit (Weeks 0 through 52).
Missing C-SSRS any visit except Visit 1	Monitor and Stats	From monitor's list; if missing C-SSRS at any visit except Visit 1

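### The C-SSRS stopping rule in Protocol 8.1.1 is mandatory in its lead-in and open in its second sentence, and SAP item D14 also flags a dose taken earlier on the day of a correct stop

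*Protocol*

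**What the plan says.** **Protocol 8.1.1, lead-in.** After the liver-test criteria, a second list opens: "In addition, patients will be discontinued from the investigational product in the following circumstances".

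**Protocol 8.1.1, C-SSRS bullet.** One item in that list begins: "The patient develops active suicidal ideation with some intent to act with or without a specific plan". It is identified by a yes to ideation question 4 or 5, and suicide-related behaviour recorded on the C-SSRS is included as well. The next sentence of the bullet recommends assessment by a psychiatrist or "appropriately trained professional to assist in deciding whether the subject is to be discontinued from the study".

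**What follows a stop.** For treatment, the end of 8.1.1 says: "Any patient who permanently discontinues the study treatment for any reason will stop treatment and continue to the ETV", with Period 3 afterwards. For the study, 8.2 says: "Any patient who discontinues the study for any reason will stop treatment and continue to the ETV prior to entering the Post-Treatment" Follow-Up Period.

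**SAP 6.17, Table RHCF.6.9, item D14.** The item repeats the trigger without the specialist sentence. Its source is both the monitor's list and programming, and the programmed part reads: "If patient still receives study treatment on the same day or after the date with a yes to question 4 or 5", or suicide-related behaviour on the C-SSRS. The note under the table says that a flag from either source is enough. D14 belongs to the important violations, in the subcategory for breaches of the discontinuation criteria.

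**The concern.** This is a safety stopping rule, so its text should lead every investigator to the same action. Here the lead-in leaves no choice about study drug, while the sentence after the trigger asks a specialist to help with a choice. An investigator whose patient has just reported suicidal intent has to work out whether the drug stop is already settled or waits for the assessment.

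The SAP then measures compliance with a rule whose meaning is unsettled. If stopping is mandatory, flagging a patient who stays on drug is right. If it follows the assessment, the same flag records as a violation something the protocol provided for. On either reading, the same-day clause catches a dose that came before the finding. The D14 count would then mix real failures to stop with correct handling.

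**Working it through.** No arithmetic applies. The check sets the texts side by side.

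**1. Is the lead-in mandatory for this bullet?** Yes. The bullet stands in the list governed by the lead-in, and the object is the investigational product.

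**2. Does 8.1.1 write discretion differently elsewhere?** Yes, in two ways.
- Liver tests have their own list outside the mandatory one. There, stopping is to be considered "by the investigator when a patient meets one of the following conditions after consultation with the Lilly-designated medical monitor".
- The malignancy bullet, inside the mandatory list, carries a written exception: "Patients may be allowed to continue if they develop no more than 2 nonmelanoma skin cancers" within a 12-month period.

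The C-SSRS bullet has neither form. It has only the recommendation of an assessment that feeds a decision.

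**3. Does drug versus study resolve it?** The lead-in says investigational product and the second sentence says study. The wording therefore allows this reading: drug stops in every case, and the specialist advises only on leaving the study. The two routes compare as follows.

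| Event | Section | Consequence |
|---|---|---|
| Permanent stop of study treatment | 8.1.1 (also 5.1.2) | Stop treatment, Early Termination Visit, Period 3 |
| Discontinuation from the study | 8.2 | Stop treatment, Early Termination Visit, Period 3 |

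The stated consequence is the same. Once drug is stopped, a separate decision on study exit would change almost nothing in what happens next. In addition, the bullet on starting another effective PsA or Ps agent, in the same product-stopping list, is itself worded as leaving the study. The word does not reliably mark a different event in this section.

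**4. Is the interval before the assessment covered elsewhere?** Section 8.1.2 allows temporary interruption for adverse events in general but does not name this situation. Section 9.4.3 describes the C-SSRS and its forms. Neither says what happens to dosing while the assessment is pending.

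**5. What does D14 flag?** Applying its programmed wording to three patients with a positive C-SSRS:

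| Patient | Lead-in alone | Discontinuation left to the assessment | D14 |
|---|---|---|---|
| Injects in the morning, positive at the visit, stopped there | Correct | Correct | Flagged |
| Injects after the positive visit, no assessment sought | Not correct | Not as recommended | Flagged |
| Kept on drug after the recommended assessment | Not correct | Open to the decision | Flagged |

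The first row is flagged although the handling is correct on both readings. The third row depends on the reading. D14 cannot tell the rows apart.

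**6. Can the data order events within a day?** The Study Drug Administration Log records date and time of injection (Protocol 7.6, SAP 6.10). Nothing in the documents shows a clock time for the C-SSRS, which Protocol Section 9 lists among the few assessments not completed electronically. D14 itself works from a date.

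**7. Where does the flag go?** SAP 6.17 provides a by-patient listing, a summary by treatment group, and additional analyses of primary and/or major secondary endpoints in patients without any, or a subset, of violations. The primary and major secondary analyses use all randomized patients with nonresponder imputation (SAP 6.12.1).

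**The case against.** The strongest reply is that no sentence says dosing may continue. The lead-in stops the drug, the second sentence concerns the study, and a site that kept dosing would breach the explicit lead-in. This is right as far as it goes. A reader might infer that the bullet permits continued dosing after the assessment, and the documents do not say so.

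The documents also keep the two events apart in places. Sections 8.1 and 8.2 are separate, SAP 6.8 counts them separately, and 8.1.3 foresees remaining in the study with or without drug, though only for inadvertently enrolled patients. Period 3 is itself study participation with C-SSRS visits. This makes the drug-versus-study reading possible. It does not give the specialist's decision a stated consequence, because 8.2 sends patients who leave the study into Period 3 as well.

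On D14, its word for continued receipt suggests dosing despite the finding, and detailed programming is left to an ADaM specification that is not part of these documents. Same-day order might be handled there, but the SAP text as written includes the same day without qualification. Conservative flagging is defensible for a safety deviation. That argues for keeping same-day doses under review, not for counting them automatically.

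A reader might also infer from Table RHCF.2.1 that same-day flags fall unevenly, because the adalimumab regimen for moderate-to-severe psoriasis doses in odd weeks while C-SSRS visits fall in even weeks. The documents do not support this. D14 compares calendar days, visits have windows of ±2 to ±4 days, and later injections are preferably given at home. A shared week is not a shared day, so no imbalance between regimens or arms is shown.

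**Conclusion.** The point holds. The C-SSRS bullet in 8.1.1 is internally inconsistent. The reading that reconciles it leaves the second sentence almost without content, so sites may apply it differently. SAP D14 programs the mandatory reading only, and its same-day clause also lists patients who were stopped correctly.

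The size is small in numbers. The documents give no expected frequency, so a few affected patients is an assumption. The effect reaches the deviation listing and summary, and possibly the additional analyses that leave out violators. It does not reach the ITT analyses of the primary and major secondary endpoints. The reason to act is clarity of a safety rule.

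The conclusion rests on the protocol and SAP text alone. Site training material or the ADaM specification could narrow it, but neither is available here. It takes no position on which clinical rule is right.

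**What to change.** 1. **Protocol 8.1.1.** Reconcile the lead-in and the second sentence of the C-SSRS bullet into one rule. It should say whether stopping study drug is automatic or follows the assessment, and what exactly the specialist helps to decide. The clinical choice is the sponsor's.
2. **SAP D14.** Align the item with that rule, including the place of the specialist step. Let the program flag doses dated after the assessment date, as far as the reconciled rule makes them violations. Send doses on the assessment date to the monitor's review, which D14 already uses as a source, and flag them only if the monitor finds a dose given after the finding and contrary to the rule.

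Same-day doses should not simply be dropped, since a dose taken after a positive C-SSRS on that day would then be missed. Nor should the program order events within the day, because no C-SSRS time is shown to be collected.

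The cost is one protocol bullet, one SAP table row and manual review of what should be a few same-day cases. No new data collection is needed for this version.

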8.1.2. Temporary Discontinuation from Study Treatment

In some circumstances, it may be necessary to temporarily interrupt treatment as a result of abnormal laboratory values (see Section 8.1.1), AEs (see Section 9.2), hypertension (see Section 9.4.5.1) abnormal hepatic laboratory values (see Section 9.4.5.2), neutropenia (see Section 9.4.5.3), hepatitis B laboratory findings (see Section 9.4.5.4), or inflammatory bowel disease (IBD) events (see Section 9.2.1.1) that may have an unclear relationship to investigational product. See Section 9.4.4.2 for details regarding managing patients who test positive for TB at any time during the study.

Patients requiring surgery at any time during the study should interrupt administration of the investigational product beginning 8 weeks before the surgery, or as early as possible within 8 weeks of surgery, and resume administration of the investigational product only after complete wound healing.

8.1.3. Discontinuation of Inadvertently Enrolled Patients

If the sponsor or investigator identify a patient who did not meet enrollment criteria and was inadvertently enrolled, a discussion must occur between the sponsor CRP and the investigator to determine if the patient may continue in the study. If both agree it is medically appropriate to continue, the investigator must obtain documented approval from the sponsor CRP to allow the inadvertently enrolled patient to continue in the study with or without treatment with investigational product.

8.2. Discontinuation from the Study

Some possible reasons that may lead to permanent discontinuation include:

- enrollment in any other clinical trial involving an investigational product or enrollment in any other type of medical research judged not to be scientifically or medically compatible with this study
- participation in the study needs to be stopped for medical, safety, regulatory, or other reasons consistent with applicable laws, regulations, and good clinical practice (GCP)
- investigator decision
 - o the investigator decides that the patient should be discontinued from the study
 - o if the patient, for any reason, requires treatment with another therapeutic agent that has been demonstrated to be effective for treatment of the study indication, discontinuation from the study occurs prior to introduction of the new agent
- subject decision
 - o the patient or the patient's designee requests to be withdrawn from the study

Any patient who discontinues the study for any reason will stop treatment and continue to the ETV prior to entering the Post-Treatment Follow-Up Period (Period 3).

8.3. Lost to Follow-Up

A patient will be considered lost to follow-up if he or she repeatedly fails to return for scheduled visits and is unable to be contacted by the study site. Site personnel are expected to make diligent attempts to contact patients who fail to return for a scheduled visit or were otherwise unable to be followed up by the site. Site personnel must, at a minimum, make 2 phone attempts and send a certified letter or its equivalent in that region.

9. Study Assessments and Procedures

Section 2 lists the Schedule of Activities, with the study procedures and their timing (including tolerance limits for timing).

Appendix 2 lists the laboratory tests that will be performed for this study.

Appendix 4 lists the hepatic monitoring tests for treatment-emergent abnormality.

All study assessments except for the C-SSRS, Self-Harm, and Self-Harm Follow-Up will be completed electronically.

For all assessments, the same assessor should perform each assessment for a given patient during the study to minimize interobserver variation.

9.1. Efficacy Assessments

9.1.1. Primary Efficacy Assessments

9.1.1.1. Combined Endpoint of American College of Rheumatology 50 Responder Index and Psoriasis Area and Severity Index 100

In order to be considered a responder to the primary efficacy measure at Week 24 in this study, a patient must simultaneously achieve both ACR50 and PASI 100 responses.

ACR50 response is an efficacy measure for which a patient must satisfy the following:

- 1) >50% improvement from baseline in TJC and
- 2) \geq 50% improvement from baseline in SJC and
- 3) ≥50% improvement from baseline in at least 3 of the following 5 ACR Core Set criteria:
 - a. Patient's Assessment of Pain Visual Analog Scale (VAS)
 - b. PatGA VAS
 - c. PGA VAS
 - d. patient's assessment of physical function as measured by the HAQ-DI
 - e. acute-phase reactant as measured by high sensitivity (assay) CRP (hs-CRP)

PASI 100 is described in Section 9.1.2.1. Patients achieving PASI 100 are defined as having an improvement of 100% in the PASI compared to baseline.

9.1.2. Secondary Efficacy Assessments

9.1.2.1. Psoriasis Area and Severity Index (PASI 75, PASI 90, PASI 100)

The PASI will be administered by a blinded assessor. The PASI is an accepted primary efficacy measurement for this phase of development of psoriasis treatments (EMA 2004). The PASI combines assessments of the extent of body-surface involvement in 4 anatomical regions (head, trunk, arms, and legs) and the severity of desquamation (scaling), erythema, and plaque induration/infiltration (thickness) in each region, yielding an overall score from 0 for no psoriasis up to 72 for the most severe disease (Fredriksson and Pettersson 1978). The PASI has been the most frequently used endpoint and measure of psoriasis severity in clinical trials (EMA 2004;

Menter et al. 2008). A clinically meaningful response is a PASI 75, which represents at least a 75% decrease (improvement) from the baseline PASI score. As minimum treatment response, the European and German guidelines mention a PASI 50 response. Higher levels of clearance (PASI 90), as well as complete resolution of psoriasis (PASI 100), have become additional endpoints because of the increasing recognition of the association of higher clearance with greater health-related QoL (Puig 2015).

Patients achieving PASI 75, 90, or 100 are defined as having an improvement of at least 75%, 90%, or 100%, respectively, in the PASI compared to baseline.

Absolute PASI scores of ≤ 1 , ≤ 2 , or ≤ 3 may be considered as treatment targets for the management of plaque psoriasis.

